## **6. Recruitment Methods**

### **6.1. Does the study involve the recruitment of participants?**

**No: If no, skip to 7.1**

**Yes: If yes; indicate how, when, where, and by whom participants will be recruited**

### Focus Group Discussions

The study team will approach community leaders that will identify TBAs who are eligible for the study and TBA delivery clients to join the study. We will aim to recruit up to 10 TBAs and delivery clients respectively. Health workers will be approached in health facilities within the same community. We will aim to recruit up to 10 health workers. Recruitment will be done by field enumerators in any of the villages in Ebonyi State, and will be conducted in July 2016.

Communities are organized differently in this context. There is often a naming ceremony held within the first week, to which everyone is invited, the TBA or nurse or midwife is lauded for successful delivery, people rub powder on their faces and give the mother gifts. Generally, delivery is celebrated like a wedding. Identifying TBAs who are eligible is akin to identifying women leaders - the community leader will help ensure that women who are not truly performing this function do not end up in our study. The write-up states we will identify TBA clients (without any comment on eligibility, which is something the study team needs to do in line with criteria above).

### Randomized Controlled Trial

The study team will purposively select 67 study villages from Ebonyi State, where the randomized controlled trial will be carried out. We will identify eligible TBAs via consultation with community leaders. These consultations will be led by field enumerators in July 2016. Health workers will be recruited from primary health care facilities in the study villages in South-Eastern Nigeria by the field work team. TBAs will provide consent to inform the study team of all delivery clients during the study, and these clients will be approached by the study team. Recruitment for the trial will commence in August 2016.

To study the outcome of postnatal care attendance, we need to know if clients delivered by TBAs attend postnatal care. We cannot know ahead of time which women will choose to deliver with the TBA versus the facility. Thus unless we could enumerate every single mother who might deliver with a TBA – which is beyond the study budget – we have to identify these clients ex post, after they have chosen to delivery with a TBA. As only the TBA can provide this information, we ask if she is willing to provide it at recruitment. If she is unwilling, she is allowed to drop out of the study. In contexts like this, given the public naming of children and celebration of childbirth, the following are often public knowledge - that a woman was pregnant, that she delivered, the approximate age of the child (and thus the date of delivery) and the address of the woman (or a landmark in lieu of her address). The piece of information that may be concerned private is the clients mobile number. TBA clients will be asked at first contact if they are willing to participate in the study and can drop out if they so desire.

**6.2. Are there any materials that will be used to recruit participants, e.g., emails, posters, and scripts?**

No  Yes: **If yes; provide a list of the materials (also include copies with the application)**

Focus Group Discussions

- Recruitment Script (Community Leader Meeting – Focus Group Discussion)
- Recruitment Script (TBA – Focus Group Discussion)
- Recruitment Script (Mother)
- Recruitment Script (Health Worker)

Randomized Controlled Trial

- Recruitment Script (Community Leader Meeting – Randomized Controlled Trial)
- Recruitment Script (TBA – Randomized Controlled Trial)
- Recruitment Script (Delivery Client)

**7. Available Resources**

**7.1. Describe the feasibility of recruiting the required number of participants within the recruitment period**

The team will spend June 2016 to August 2016 in Nigeria laying the groundwork for the study, that is obtaining the Harvard and local ethical review, obtaining permission from the state health facility board to meet with facility heads and use facility data, meeting with community leaders, selecting study sites in partnership with local leadership in communities and facilities, and hiring and training the study team. We will collaborate with Health Policy Research Group, University of Nigeria, which has extensive research and training experience in program evaluation within the study area, and will oversee the field research activities and administration of the intervention. Recruitment for the study will begin in July 2016 and we anticipate will continue until September 2016.

**7.2. Describe how the Principal Investigator will ensure that a sufficient amount of time will be devoted to conducting and completing the research**

A member of the study team is a doctoral student that has completed all other thesis papers, and will be focused on this project for the rest of her doctoral program, spending June 2016 to September 2016 in Nigeria and monitoring activities closely after that.

**7.3. Are there research staff members, in addition to the Principal Investigator?**

No: **If no, skip to 7.5**

Yes: **If yes; outline training plans to ensure that research staff members are adequately informed about the protocol and study-related duties**

### Harvard-based Study Partners

The Harvard research team assisted in the development of the research protocol and assigning study-related duties.

### Local Study Partners

Field work training will help to ensure that enumerators are trained to the same standards to minimize variation that may occur during the data collection exercise. While training focuses on thoroughly familiarizing enumerators with the questionnaire, it also asks that enumerators understand research ethics and how to create an atmosphere in the interview process that allows respondents to feel comfortable in answering sensitive questions. We will also teach enumerators how to emphasize the confidentiality of the interview and how to obtain the respondent's informed consent to participate in the study in a non-coercive manner. It will be the responsibility of the principal investigator and field work manager to train field work enumerators. The enumerators practice interviews will serve as pre-tests of both versions of the questionnaire – English and Igbo language. Debriefing sessions will capture feedback on translations. Training will occur over two days.

#### **7.4. Describe the minimum qualifications for each research role (e.g., RN, social worker) their experience in conducting research, and their knowledge of local study sites and culture**

##### A. Field Work Enumerator

#### Tasks

1. Participate fully in field work training
2. Assist field work manager and principal investigator in all activities related to the project – including data collection, pre-tests, study pilots, and participant enrollment
3. Travel to study districts and other duties as necessary

#### Job Requirements

1. Secondary school or higher education from a recognized school
2. Prior experience collecting survey data with study partner, Health Policy Research Group
3. Fluent in English and Igbo Languages
4. Comfortable communicating with key study stakeholders – mothers, traditional birth attendants, health workers, community leaders, and policy makers

##### B. Field Work Manager

#### Tasks

The person will report to and work with the principal investigator to perform a variety of tasks including but not limited to:

1. Supervise the implementation of field operations for the pre-test, pilot, and project, in South-Eastern Nigeria
2. Manage the team of field work enumerators in supporting field operations
3. Ensure compliance with ethical standards and data management procedures for the study
4. Manage systems and processes for tracking and monitoring survey activities and report to the principal investigator on a frequent basis
5. Lead focus group discussions
6. Work with principal investigator to train field work enumerators
7. Manage and appropriately document field team expenditure, supported by receipts
8. Store and safely keep all study equipment including android tablets and audio recording devices

#### Job Requirements

1. Master's degree in public health or related field
2. Full-time staff of the study partner, Health Policy Research Group
3. At least 3 years of experience in implementing field operations for multiple projects

4. Prior experience in the use of android devices for data collection, research compliance, and data security protocols
5. Familiarity with randomized controlled trials and focus group discussion methods
6. Excellent communication skills/ fluency in English
7. Fluency in reading, writing and speaking Igbo Language
8. Excellent management and organizational skills

C. Translator

Tasks

1. Attend an initial conceptualization and familiarization meeting, a synchronization meeting, and a pre-test meeting in connection with the survey and focus group discussion tool translation
2. Translate surveys and focus group discussion tools into Igbo language as used in day-to-day conversations

Job Requirements

1. At least 5 years of experience in Igbo translation
2. Preferably, a journalist working in a local translation

As translator will be hired by the local implementing partner. When the translator is hired, a locally approved version of the signed translation attestation form will be attached as a modification with the name of the translator.

**7.5. Briefly describe how the research facilities and equipment at the research site(s) support the protocol's aims, e.g., private rooms available for interviews, etc.**

Focus Group Discussions

Focus group discussions will hold in secluded, quiet locations identified in the community by the study team and community leadership

Randomized Controlled Trial

In-person surveys will be conducted in a convenient location decided by the respondent at recruitment.

**7.6. Are there provisions for medical and/or psychological support resources (e.g., in the event of incidental findings, research-related stress)?**

No  Yes: If yes; describe the provisions and their availability

In the event of research-related stress, study participants will be referred to the hospital affiliated with the local implementing partner (University of Nigeria Teaching Hospital) for counselling.

**8. Vulnerable Populations**

**8.1. Are there any potentially vulnerable populations (e.g., children, pregnant women, human fetuses, neonates, prisoners, elderly, economically disadvantaged, employees or students of the investigator or sponsor, undocumented, terminally ill, cognitively impaired or mentally ill, etc.)?**

No: If no, skip to 9.1

Yes: If yes; identify all vulnerable populations

The study may involve data collection from individuals who are unable to communicate in English language.

**8.2. Describe safeguards to protect their rights and welfare**

We will translate all data collection tools and consent forms into the local language (Igbo) so that participants understand the terms of participation and can fully engage in the study. Focus group discussions and interviewer-led surveys will be facilitated by study staff who can converse fluently in the local language, have collected data in this setting before, and who are trained to elicit consent appropriately irrespective of literacy. A signed translation attestation form will be attached to this application as a modification.

## 9. Consent Process

### 9.1. Will consent to participate be obtained?

No: If no, skip to 9.5

Yes: If yes; describe the setting, role of individuals involved, timeframe(s), and steps to minimize coercion/undue influence during the consent process (at the time of initial consent and throughout the study)

#### Focus Group Discussions

Informed consent will be obtained by field enumerators. Given the varying literacy level of the target population, the consent form will be delivered orally in the preferred language (English or Igbo language) and a signature will be asked for. The consent discussion will last about 20 minutes and be followed by an invitation to the venue for the focus group discussion at a later date. The field enumerators will be trained to avoid coercion during the consent process. Study staff will continue to ensure participants understand what the research is about and what their participation involves. There will be numerous opportunities during recruitment and obtaining informed consent for participants to opt out of the study. Any new information which might influence a participant's decision to continue participation will be provided to participants including re-consent.

Attached:

- Focus Group Discussion Consent Form – TBA delivery client
- Focus Group Discussion Consent Form - TBA
- Focus Group Discussion Consent Form – Health Worker

#### Randomized Controlled Trial

Informed consent will be obtained by field enumerators. In the case of TBA delivery clients, the consent form will be delivered orally in the preferred language (English or Igbo language). A signature will be asked for, for in-person interviews in the case of TBAs. The consent discussion will last about 20 minutes. Potential participants will be given the opportunity to opt out, postpone the decision about joining, consent and postpone the survey, or consent and partake in a survey. The field enumerators will be trained to avoid coercion during the consent process. Study staff will continue to ensure participants understand what the research is about and what their participation involves. There will be numerous opportunities during recruitment and obtaining informed consent for participants to opt out of the study. Any new information which might influence a participant's decision to continue participation will be provided to participants including re-consent.

Attached:

- Randomized Controlled Trial Consent Form – TBA
- Randomized Controlled Trial Consent Form – TBA Delivery Client (verbal consent only via phone)

We will provide each participant with the contact information of a local research team member to communicate their request to have results sent to them when available.

### 9.2. Are there any special populations?

No  Yes: If yes; describe the process to obtain consent, permission or assent

**9.3. Will consent of the participants be documented in writing?**

Yes  No: **If no; describe the rationale for requesting a waiver or alteration of documentation of consent (and/or parental permission)**

Consent will be collected verbally for TBA delivery clients in the RCT. In all other cases – TBA in FGDs, Health worker in FGDs, TBA delivery clients in FGDs, TBA in RCT – consent will be collected in person.

**9.4. Will participants be provided with a copy of their signed consent form or information sheet (when a consent form is not signed)?**

Yes  No: **If no; explain any extenuating circumstances that make it impossible or inappropriate to meet this requirement, i.e., doing so may place participants at increased risk, if inadvertently disclosed**

In all cases where consent is collected in writing, participants will be provided with a copy of their signed consent form. In one case, for TBA delivery clients in the RCT, consent will be elicited over the phone. In this case, participants will not receive a copy of their signed consent form unless they request it.

**9.5. Is a waiver or alteration of consent (and/or parental permission) being requested?**

No  Yes: **If yes; describe the rationale for the request. If the alteration is because of deception or incomplete disclosure, explain whether and how participants will be debriefed (include any debriefing materials with the application)**

Randomized Controlled Trial

The consent form for the TBAs will not include information on the referral incentive intervention. The intervention offers TBAs in the referral incentive arm an incentive for referring mothers to postnatal care in facilities. Informing TBAs in the control arm about this incentive during informed consent at baseline will have negative consequences, and the research cannot be practicably carried out without this alteration. TBAs in the control arm receive information on the need for postnatal care and an incentive for reporting each client they deliver (TBAs in the referral incentive arm receive what the control arm receives in addition). We will be unable to measure the pure effect of incentives and will instead capture the effect of receipt of incentives by referral incentive TBAs and anger or collusion by control TBAs in response to exclusion from receiving the referral incentive. We can thus not answer the research question intended. The information that will be elicited during the randomized controlled trial do not constitute more than minimal risk to subjects. This information is common knowledge in the community including TBA service patterns, demographic information, delivery client base etc.

Debriefing

All TBAs will be provided with additional information on the intervention when all follow-up survey data has been collected using the attached debriefing script. Each TBA will be approached in her home (which often doubles as the work place) within the community by one of the field enumerators. We will provide information on the incentive used in the study, the probability of selection into each study arm, and the opportunity to drop out of the study if so desired.

In addition, contact information of TBA delivery clients will be given by TBA to the study team prior to initial contact with delivery clients. This information will be collected via follow-up survey tools. This is akin to the receipt of contact information for TBA from community leaders prior to initial contact by study team from a cultural standpoint – the TBA is not a health worker. She is one community member with no training providing a service to another community member. Everyone knows her, and many women deliver with her. I could for example, collect this information from the community leader or women leader instead of the TBA – and they would probably know who had just delivered and potentially where.

To try and inform delivery clients ahead of time of the possibility of their contact information being shared and being contacted by the research team for recruitment into the study, we can hold a village meeting in every village we do the study in and inform everyone about the study. We cannot know every woman who will visit a TBA ahead of time, she may come from a village in which we have no selected TBA, but this would ensure we've tried to inform as many possible participants ahead of time.

We cannot anticipate which women will visit the TBA (rather than the clinic) ex-ante and obtain informed consent beforehand. Constraints in study funding also prevent the enrollment of all pregnant women in every study village at baseline. Nevertheless, the receipt of services from the TBA by clients is often common knowledge in these communities (see below) so that this information is unlikely to constitute more than minimal risk to clients. Delivery clients will be given the opportunity to opt out of the study at multiple points – enrollment, during elicitation of consent, during the follow-up survey, and after the survey. When informed consent is elicited by study enumerators, delivery clients will be intimated on how their contact information was obtained – that is they will be informed explicitly that the study team is contacting them based on patronage of a TBA who gave the team their contact information.

The ceremony surrounding the birth of a child in these contexts implies the community knows the woman was pregnant, has delivered a baby, was delivered by a TBA (who is often involved in the naming ceremony and sometimes gives the child one of her/his names), and where she lives (because they all come for the ceremony – anyone who hears can stop by and eat food/bring a gift etc.). The phone # is the one piece of information that may be private (primarily because that is not typically how people contact each other). We will allow both her TBA and herself to opt out if they consider this an invasion of privacy.

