6.	Clients may be concerned that TBAs will provide contact information of delivery clients to the study team to ascertain the study outcome - the incidence of postnatal care referrals.	This is the basis for potential inclusion of clients. In this context, the following are often public knowledge in the community - that a client is pregnant, that she has delivered a child, that she delivered with a TBA, the approximate date of delivery, and her address. A contact phone number might however not be public knowledge and a cause of concern.	We will select TBAs whose relationship with their clients allows them to share this information with the study team. Both TBAs and delivery clients will be allowed to opt out of the study at any point if privacy is a concern, and their information will not be used if they do, nor will they face any penalty for dropping out.

**10.2. Identify whether any of the information collected, if it were to be disclosed outside of the research, could reasonably place the participant at risk of criminal or civil liability or be damaging to the participant’s financial standing, employability or reputation.**

No, we anticipate that information collected is largely common knowledge within these communities related to maternal delivery service choices and the livelihoods of traditional birth attendants.

As the TBA does not have an employer per se (she is a woman who in her home or her church delivers women), she has no formal training and no supervisor. She is often mentored by another TBA who does not owe her a salary and to whom she does not pay a salary. Her services are many times unremunerated. She is given payment or gifts depending on the ability of her clients.

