### **14. Participant Privacy**

#### **14.1. Describe provisions to protect participants' privacy (their desire to control access of others to themselves, e.g., the use of a private interview room) and to minimize any sense of intrusiveness that may be caused by study questions or procedures**

Group and individual interviews will be conducted in a private place, at the participant's convenience.

In the randomized controlled trial, we will ask TBAs to give us the names, addresses, and phone numbers of clients they deliver on a two-weekly basis. Follow-up calls to these clients will involve eliciting consent for inclusion in the study and ascertaining that delivery and referral by the TBA occurred. That is, we obtain information on the primary outcome of the study through follow-up surveys with TBA clients. Self-reports by TBAs given the incentives offered are likely to be unreliable.

The procedure of informed consent will be non-coercive and conducted in the language of choice for both the TBA and her clients. In these settings, it is not generally private information that a woman was pregnant, where she lives, and that she has delivered, and where she delivered. However, we will allow both the TBA and her clients to opt out of the study at any point that they consider the study procedures intrusive. The TBA and her clients will be informed of this provision. As long as drop-out of the study is non-differential across arms and is not in high proportions, this will not affect our ability to estimate effects.

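### Drop-out is offered at debriefing, after outcomes are collected and the arm is known, with no rule on keeping the data, so data could be lost unevenly by arm from the intention-to-treat analysis

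*Protocol*

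**What the plan says.** Protocol 9.5 asks for an alteration of consent: "The consent form for the TBAs will not include information on the referral incentive intervention". Incentive-arm TBAs learn of the payment when it is offered to them (Protocol 4.6). Controls are first officially told at debriefing.

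Debriefing covers all TBAs and takes place "when all follow-up survey data has been collected using the attached debriefing script". On its content the protocol says: "We will provide information on the incentive used in the study, the probability of selection into each study arm". The same sentence adds "the opportunity to drop out of the study if so desired". It does not say what dropping out at that stage means for data already held.

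The only stated consequence of opting out is in Protocol 10.1, in the risk-table row on clients' contact details. TBAs and clients may "opt out of the study at any point if privacy is a concern, and their information will not be used if they do".

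Protocol 14.1 makes valid estimation of the effect conditional: "As long as drop-out of the study is non-differential across arms and is not in high proportions, this will not affect our ability". No rule follows for the case where the condition fails.

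Protocol 5.1 and section 1 of the SAP's Proposed Empirical Models both name an intention-to-treat effect of the incentive on the proportion of clients referred. Neither contains a withdrawal rule, a report of withdrawals by arm, or a sensitivity analysis for removed TBAs.

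**The concern.** An intention-to-treat comparison needs the outcomes of everyone randomised. Here an exit is offered when all outcomes exist, together with information that reveals the arm and is new and possibly unwelcome mainly to controls. With follow-up finished, drop-out can hardly affect the analysis except by taking collected data out of it.

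If controls use the exit more than incentive-arm TBAs, and if those who leave differ in their referral proportion, the treatment coefficient is biased. High-referring controls leaving would inflate it; low-referring controls leaving would shrink it. The planned regression would show neither, and section 14.1 offers only the assumption that this does not happen. Enrolling more TBAs would not help, because this is bias and not imprecision.

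**Working it through.** **Inputs from Protocol 5.2:** target difference 0.20, SD 0.37, two-sided alpha 0.05, two equal arms, minimum 160 TBAs (80 per arm).

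**Assumptions:** the documents give no withdrawal rate, no control mean and no account of who would leave. The control mean of 0.30, the share removed d and the selection gap g below are illustrative. Only controls are removed.

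**1. The plan's sample size.** n per arm = 2 × 0.37² × (1.960 + 1.282)² / 0.20² = 71.9, so 72 per arm or 144 in total. The plan states 160, which is on the safe side. Power at 80 per arm is 92.8%. This gap has no bearing on the point; 80 per arm is used only to set the scale.

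**2. Standard error.** 0.37 × √(1/80 + 1/80) = 0.0585, about 0.059.

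**3. Precision is not the issue.** Losing 10% of controls leaves 72 against 80. The standard error becomes 0.37 × √(1/72 + 1/80) = 0.0601 and power falls only from 92.8% to 91.4%. Losing 20% gives 89.7%.

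**4. Worst-case bias.** Take control proportions as a Beta distribution with mean 0.30 and SD 0.37. Its parameters sum to 0.30 × 0.70 / 0.37² − 1 = 0.534, giving 0.160 and 0.374. Remove a share d entirely from one end. Change in effect = 0.30 − mean of retained controls.

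| Removed | Retained mean, highest removed | Shift | Retained mean, lowest removed | Shift |
|---|---|---|---|---|
| 5% | 0.263 | +0.037 | 0.316 | −0.016 |
| 10% | 0.2235 | +0.077 | 0.333 | −0.033 |

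At 10% removed, control means from 0.20 to 0.50 give upward shifts of 0.055 to 0.089 and downward shifts of 0.022 to 0.055.

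**5. Milder selection.** Let g be the mean of removed controls minus the mean of retained controls. The full control mean is d × (removed mean) + (1 − d) × (retained mean), so it exceeds the retained mean by d × g. That is the bias in the treatment difference.

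- d = 10%, g = 0.10: 0.10 × 0.10 = 0.010
- d = 10%, g = 0.37 (one SD): 0.10 × 0.37 = 0.037

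The sign follows the sign of g. With the standard error from step 3, these are 0.010 / 0.0601 = 0.17 and 0.037 / 0.0601 = 0.62 standard errors. If the true effect were zero, the two-sided type I error would be 5.3% and 9.4% in place of 5%.

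**The case against.** **The data-not-used rule is not in the debriefing text.** This is true. It stands in section 10.1 and is tied to privacy. A reader might infer that the protocol orders deletion for any TBA who drops out at debriefing; it does not. What stands is that this is the only consequence stated anywhere, that it applies at any point, and that no alternative is given for drop-out after follow-up.

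**The primary outcome comes from clients.** Clients are surveyed by telephone and give their own verbal consent (Protocol 4.6, 9.1, 9.3). Nothing says that a TBA's withdrawal removes her clients' answers. This is a fair objection, and it helps the fix, since those answers are natural candidates for retention. But the outcome is a proportion per TBA, and the documents do not say whether that row survives her withdrawal.

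**The protocol does not predict withdrawal by controls.** A reader might take "anger or collusion by control TBAs in response to exclusion from receiving the referral incentive" as such a prediction. The phrase concerns disclosure at baseline and its effect on behaviour during the trial. It shows that the authors expect exclusion from payment to matter to controls, and debriefing reveals that exclusion. It does not show that controls will leave, or that high referrers would be the ones to do so.

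**The attached debriefing script and consent forms may define drop-out.** They were not available for this review, and their absence is not a gap in the plan. The analysis rule still belongs in the protocol and SAP.

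**Withdrawal after incomplete disclosure is an ethical safeguard.** Agreed. The offer itself is not criticised.

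**Conclusion.** The point holds as a conditional one. The stated sections, read together, allow outcome data to be removed after the arm is known, possibly more among controls, and nothing in the plan would detect or bound the result. That would undo both the condition in section 14.1 and the intention-to-treat claim.

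For a 10% loss confined to controls, the shift lies between −0.03 and +0.08 at the extremes and is about 0.01 to 0.04 in size under milder selection, against a standard error of about 0.059 and a target of 0.20. A reader might infer that more than a third of the target effect is at risk (0.077 / 0.20 = 38%). That figure requires every departing control to be among the highest referrers, no incentive-arm TBA to leave, and the assumed mean and withdrawal rate. It is a bound, not an expectation. If few TBAs withdraw, the effect is small. The documents support no statement about direction.

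The change should be made because it protects the stated estimand at low cost, and because a rule chosen after debriefing would be post hoc.

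**What to change.** 1. **Protocol 9.5 and the debriefing form.** Keep the offer, but record two separate choices: no further participation or contact, and deletion of data. Retain outcome data already collected, including answers from separately consenting clients, unless deletion is requested, and as far as the ethics committees allow. Say how this relates to the privacy opt-out in section 10.1.
2. **Reporting.** Give the number of TBAs withdrawing and the number deleting data, by arm, before and after debriefing.
3. **SAP section 1.** If any data are deleted, add a pre-specified sensitivity analysis for the treatment coefficient, such as best/worst-case or trimming (Lee) bounds. State that Lee bounds assume monotone selection and apply to TBAs who would remain under either arm, so they do not recover the full intention-to-treat effect. Best/worst-case bounds do cover all randomised TBAs but will be wider.
4. **Protocol 14.1.** Replace the assurance with this rule.

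The cost is one extra line on the debriefing form, the ethics committees' agreement to it, and one sensitivity analysis if data are deleted. If no one withdraws, the primary analysis is unchanged.
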